3.2 General study level definitions

3.2.1 Analysis visits

All data will be analyzed based on the visits identified per the Schedule of Activities in protocol. Mapping to analysis visit windows is not applied, except for PEOT visit (specified in [Section 3.2.3](#)).

3.2.1.1 Relative day

Relative day for an event will be derived with the date of the first sc infusion of Investigational Medicinal Product (IMP) in MG0007 as reference.

Relative days for an event of measurement occurring before the date of first sc infusion will be prefixed with '-' and are calculated as follows:

$$\text{Relative Day} = [(\text{Event Date} - \text{Date of First Infusion})]$$

Relative days for an event or measurement occurring on or after the date of first sc infusion are calculated as follows:

$$\text{Relative Day} = [(\text{Event Date} - \text{Date of First Infusion}) + 1]$$

For events or measurements occurring after the date of the last sc infusion, relative day will be prefixed with ‘+’ in the data listings and are calculated as follows:

$$\text{Relative Day} = + [(\text{Event Date} - \text{Date of Last Infusion})]$$

There is no relative Day 0. Relative day is not calculated for partial dates in cases where relative day is shown in a participant data listing. In such cases, relative day should be presented as ‘--’ in the participant data listings.

3.2.2 Study periods

The study cycle consists of the following:

- Treatment Period: 6 weeks
- Observation Period: 16 weeks
- Non-treatment period

The following definitions for starting and entering the study periods for each cycle will be applied:

- **Treatment Period** starts with the first day of IMP in each cycle in MG0007 and ends after Day 43 or PEOT assessments. All participants in the Safety Set will be considered to have started the Treatment Period. A participant is considered to have completed the Treatment Period of each cycle if assessments from Treatment Period Day 43 are completed.
- **Observation Period** starts with one day after the end of the Treatment Period of each cycle and ends after the final assessments at Day 155 visit. Participants with assessment on any Observation Period day are considered to have started the Observation Period.
- **Non-treatment period** starts with one day after the end of the Observation Period of each cycle and ends before the start of next cycle or the EOS assessment.

A study participant is considered to have completed the study if he/she has completed all phases of the study including the Observation Period and the EOS visit assessments. The end of the study is defined as the date of the last visit of the last participant in the study.

3.2.3 Mapping of assessments performed at Premature End of Treatment Visit

PEOT assessments will be assigned to the next scheduled site visit (following the last scheduled visit that the participant completed prior to PEOT) where each assessment is evaluated as per protocol. This approach means that there is a chance that PEOT data will be mapped to different visits according to the schedule of assessments.

3.3 Definition of Baseline values

For the analyses done by entire study, Baseline values will be the last available value prior to or on the same date of first administration of IMP in MG0007. Scheduled or unscheduled measurements can be used as the Baseline value.

For the analyses done by study cycle, Baseline values will be defined as the last available value prior to or on the same date (and same time if time is collected for the individual assessment) of first administration of IMP at each cycle (ie Baseline [Day 1]) value for that cycle.

In case of baseline of specific cycle is missing, values from previous cycle or previous studies EOS visit will be considered as baseline for that cycle.

For [REDACTED] Baseline values will be the Baseline values determined in MG0003.

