9.2 General statistical considerations

Statistical evaluation will be performed by the Sponsor or designee and supervised by the Exploratory Statistics Department of UCB. For safety analyses, data will be summarized by dose levels of rozanolixizumab at the time of the event or measurement. For efficacy, data will be summarized by the dose first received in the study. Additionally, efficacy data will be summarized by dose levels of rozanolixizumab received in each treatment cycle.

All analyses will be performed using Statistical Analysis System (SAS[®]) version 9.3 or later (SAS Institute, Cary, NC, USA). Continuous variables will be summarized by visit (where applicable) with the statistics including the number of study participants (n), mean, standard deviation (SD), median, minimum, and maximum. Categorical variables will be summarized by visit (where applicable) with frequency counts and percentages.

If not otherwise stated, Baseline values will be the last available predose value, or in the case of analyses done by 6-week treatment cycle, Baseline will be defined as the Baseline (Day 1) value for that cycle. This will be clearly defined in the SAP. All relevant data will be listed by treatment group and study participant.

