9.2.1 Intercurrent event handling rationale and impact on the study

In MG0007, every study participant, except those coming from MG0004, will start with an initial fixed mandatory cycle. Prior to dosing in the initial fixed treatment cycle, the study participant will be assessed for MG worsening (eg, an increase of 2.0 points on the MG-ADL or 3.0 points on the QMG scale). The study participant will be initially randomized to rozanolixizumab equivalent to approximately 7mg/kg or 10mg/kg weekly (QW). After the first treatment cycle, dose adjustments may be applied at the start of each treatment cycle based on Investigator's discretion. Dose adjustments may not be applied during a treatment cycle.

For the assessment of safety and tolerability, adverse events (AEs) recorded up to 8 weeks after the last sc infusion will be utilized for main analyses, regardless of study participants receiving treatment with rescue therapy.

For the analyses of efficacy endpoints, the intercurrent events to be considered are the use of rescue therapy prior to Day 43 and permanent treatment discontinuation (or withdrawal from study) due to TEAEs. Efficacy endpoints will be summarized in line with a treatment policy approach. With this approach, rozanolixizumab results will be analyzed regardless of study participants receiving treatment with rescue therapy. Summaries will also be presented for the efficacy endpoints where participants will be censored at the time that they take rescue medication.

Missing values will not be imputed.

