9.4 Planned efficacy and other analyses

9.4.1 Efficacy analyses

The main efficacy endpoint is the "Change from Baseline (Day 1) to Day 43 in MG-ADL score," for each of the first three 6-week treatment cycles where the Baseline of the respective cycle will be used as reference.

The summaries will be provided overall and by randomized treatment in-line with a treatment policy approach. Observed results will be presented for the different cycles (1 to n) regardless of the first cycle being mandatory or not. Missing values will not be imputed. Further summaries will be presented by the treatment received in each cycle.

The other secondary efficacy endpoints, Change from Baseline (Day 1) to Day 43 in QMG score, Change from Baseline (Day 1) to Day 43 in MG-C score, Change from Baseline (Day 1) to Day 43 in MG Symptoms PRO 'Muscle Weakness Fatigability' score, Change from Baseline (Day 1) to Day 43 in MG Symptoms PRO 'Physical Fatigue' score, and Change from Baseline (Day 1) to Day 43 in MG Symptoms PRO 'Bulbar symptoms' score, will be analyzed in the same way as the main secondary endpoint based on the MG-ADL.

Time to MG-ADL response (≥ 2.0 -point improvement from Baseline [Day 1]) for each treatment cycle will be summarized using time-to-event methodology (Kaplan Meier).

The time between consecutive treatment cycles will be summarized in order to provide information on how long the effect of rozanolixizumab lasts, ie, how long it will take to introduce a new cycle.

The number and percentage of participants achieving Minimal Symptom Expression (MG-ADL score of 0 or 1) at any time during the Treatment and Observation Periods will be summarized by cycle and by dose administration in that cycle.

Additionally, the number of treatment cycles will be summarized by treatment group.

Further summaries will be described in the SAP.

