9.6 Handling of dropouts or missing data

All imputation of missing or partial dates for safety assessments, as well as handling missing efficacy data (where applicable), will be detailed in the SAP.

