3.9 Changes to protocol-defined analyses

In the protocol section 9.2.1, the intercurrent events to be considered are the use of rescue therapy prior to Day 43 and permanent treatment discontinuation (or withdrawal from study) due to TEAEs. In the SAP, we consider use of rescue therapy prior to Day 43 and permanent treatment discontinuation due to TEAEs as intercurrent events.

In the protocol, the treatment policy strategy is described for the analysis meaning that all data was planned to be analyzed regardless of study participants receiving treatment with rescue therapy. Summaries will also be presented for the efficacy endpoints where participants will be censored at the time that they take rescue medication. In the SAP, time to MG-ADL response will be analyzed censoring the data at the time of the use of rescue therapy and all other efficacy endpoints will be summarized following treatment policy.

Protocol amendment 3 did not mention how to treat IgG when participants receive rescue therapy. In the SAP, the IgG values up to and including 8 weeks after start date of rescue therapy will be excluded from the analysis.

In the protocol section 8.3.1, Hy's law is defined as $>3 \times \text{ULN}$ ALT or AST with coexisting $>2 \times \text{ULN}$ total bilirubin in the absence of $<2 \times \text{ULN}$ ALP, with no alternative explanation for the biochemical abnormality (ie, without waiting for any additional etiologic investigations to have been concluded). In this SAP, Hy's law is defined as (AST or ALT $\geq 3 \times \text{ULN}$) and TBL $\geq 2 \times \text{ULN}$ and ALP $< 2 \times \text{ULN}$ to be consistent with Rozanolixizumab program SAP.

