13.2 Myasthenia Gravis-Composite scale

The MG-C score items and associated scores are provided in [Table 13–2](#).

The MG-C score comprises 10 items, each of which is weighted differently in the calculation of the overall score. The overall score ranges from 0 to 50, with a higher score indicating more severe disease.

The total score is obtained by summing the responses to each individual item.

The total score (excluding ocular items) is calculated by summing the last 7 items, excluding ptosis, double vision, and eye closure. The score ranges from 0 to 41.

In the event of missing data at a particular visit, the MG-C score will not be calculated. Due to the different weighting applied to each item it is not possible to impute the missing data with the average score across the remaining items. If baseline total score of a cycle is missing, the previous last non-missing total score (from previous cycle or study) will be considered as baseline.

Table 13–2: MG-C score items and scoring algorithm

Item	Result/Grade	Result/Grade	Result/Grade	Result/Grade
Ptosis, upward gaze (physician examination)	>45 seconds/0	11-45 seconds/1	1-10 seconds/2	Immediate/3
Double vision on lateral gaze, left or right (physician examination)	>45 seconds/0	11-45 seconds/1	1-10 seconds/3	Immediate/4
Eye closure (physician examination)	Normal/0	Mild weakness (can be forced open with effort)/0	Moderate weakness (can be forced open easily)/1	Severe weakness (unable to keep eyes closed)/2
Talking (patient history)	Normal/0	Intermittent slurring or nasal speech/2	Constant slurring or nasal but can be understood/4	Difficult to understand speech/6
Chewing (patient history)	Normal/0	Fatigue with solid food/2	Fatigue with soft food/4	Gastric tube/6
Swallowing (patient history)	Normal/0	Rare episode of choking or trouble swallowing/2	Frequent trouble swallowing eg, necessitating changes in diet/5	Gastric tube/6
Breathing (thought to be caused by MG)	Normal/0	Shortness of breath with exertion/2	Shortness of breath at rest/4	Ventilator dependence/9
Neck flexion or extension (weakest) (physician examination) ^a	Normal/0	Mild weakness/1	Moderate weakness (ie, 50% weak, +/-15%)/3	Severe weakness/4
Shoulder abduction (physician examination) ^a	Normal/0	Mild weakness/2	Moderate weakness (ie, 50% weak, +/-15%)/4	Severe weakness/5
Hip flexion (physician examination) ^a	Normal/0	Mild weakness/2	Moderate weakness (ie, 50% weak, +/-15%)/4	Severe weakness/5

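### A missing cycle baseline is filled from an earlier cycle or study with no age limit, so a cycle's change can compare two end-of-treatment scores

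*SAP*

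**What the plan says.** - **SAP 3.3.** For by-cycle analyses, baseline is the last available value up to the first dose of that cycle, equated with that cycle's Day 1. Then: "In case of baseline of specific cycle is missing, values from previous cycle or previous studies EOS visit will be considered as baseline". No maximum age is given. The text does not choose between the earlier cycle's Day 1, Day 43 or last score. The sentence before it has no earliest date either.
- **SAP 13.2.** The MG-C total is not calculated when data are missing at a visit. If a cycle's baseline total is missing, "the previous last non-missing total score (from previous cycle or study) will be considered as baseline".
- **Protocol 9.2.** "in the case of analyses done by 6-week treatment cycle, Baseline will be defined as the Baseline (Day 1) value for that cycle", followed by "This will be clearly defined in the SAP".
- **Protocol 9.4.1.** The main efficacy endpoint is defined for each of the first three cycles, "where the Baseline of the respective cycle will be used as reference".
- **Protocol 9.2.1.** "Missing values will not be imputed"; 9.4.1 repeats this.
- **Protocol 9.6.** "handling missing efficacy data (where applicable), will be detailed in the SAP".
- **SAP 3.9**, headed "Changes to protocol-defined analyses", lists several departures from the protocol but not this one.

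**The concern.** Carrying an earlier value forward is defensible when the patient's state is stable. Here the design makes it unstable: after the mandatory first cycle of MG0003 entrants, a cycle starts because symptoms have worsened (Protocol 4.1). The cycle's change is meant to measure the recovery from that worsening. A score taken before the worsening belongs to a different disease state.

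Change from cycle baseline to Day 43 over the first three cycles, and response derived from it, make up most of the secondary efficacy endpoints. Because 3.3 does not name the value to borrow, two programmers could follow it correctly and get different results. SAP 4.7 plans no sensitivity analysis, so the effect would not show.

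**Working it through.** The plan gives no figure to reproduce: there is no formal sample size, no testing, and no stated rate of missing baselines. The check uses the visit schedule and simple arithmetic.

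**1. Earliest standard restart.** The last dose is at nominal Day 36 (Table 1-3, Visit 6). The minimum interval is 4 weeks after it (Protocol 4.1): 36 + 28 = Day 64.

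**2. Restarts whose last scheduled score is the previous cycle's Day 43.** Inclusive span = last day − first day + 1, on nominal days.

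| Instrument | Scheduled after Day 43 | Restart days | Span |
|---|---|---|---|
| MG-ADL, Table 1-3 | 71, 99, 127, 155, then every off-treatment visit | 64–70 | 7 |
| MG-C and QMG, Table 1-3 | 99, 155, then 12-weekly | 64–98 | 35 |
| MG Symptoms PRO, Table 1-3 | none through 155, then 12-weekly | 64–155 | 92 |
| MG-C, Table 1-2 | 71, 99, 155 | 64–70 | 7 |
| QMG, Table 1-2 | 71 (optional), 99, 155 | 64–70, or 64–98 if Day 71 is skipped | 7 or 35 |
| MG Symptoms PRO, Table 1-2 | 99 | 64–98 | 35 |

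The Table 1-2 rows apply to the second cycle of MG0003 entrants. Protocol 8 does not require any efficacy scale at an Unscheduled Visit, so an extra score may not exist. At a Day 64 restart a Day 43 score is 64 − 43 = 21 days old; at Day 98 it is 98 − 43 = 55 days old.

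**3. Effect on one participant-cycle (assumed MG-C scores).** The previous cycle goes from 17 on Day 1 to 12 on Day 43. In the new cycle the true Day 1 score is 15, but data are missing and no total is calculated. Day 43 is 12. The responder threshold is 3 points (SAP 9.8).

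- True change: 12 − 15 = −3, a responder.
- SAP 13.2 rule, borrowing the previous Day 43: 12 − 12 = 0, a non-responder.
- For a scale governed by 3.3 alone, the same scores with the previous Day 1 borrowed: 12 − 17 = −5.

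**4. Effect on a cycle summary.** Shift in mean change = share of participant-cycles filled × gap. With the gap of 15 − 12 = 3 points, all in one direction, and assumed shares:

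- 1%: 0.01 × 3 = 0.03 points
- 5%: 0.05 × 3 = 0.15 points
- 10%: 0.10 × 3 = 0.30 points

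The responder rate moves by at most the share itself: 1, 5 or 10 percentage points.

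**The case against.** **The protocol delegates this to the SAP.** It does, in 9.2 and 9.6, so a SAP rule on baselines is allowed. A reader might infer that the SAP breaches the protocol; that goes too far. What remains is an unlisted departure: SAP 14.2 itself describes the addition to 13.2 as an imputation rule, while the protocol says that missing values are not imputed.

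**The exposure is narrow.** This largely stands. Visit 1 of a subsequent cycle is a site visit with all these scales scheduled, and QMG is not optional there. QMG and MG-ADL totals survive one or two missing items (SAP 13.1, 13.3), and MG Symptoms PRO scales need 70% of items (13.4). MG-C has no such tolerance. The spans in the table are calendar days on which the problem can arise, not frequencies.

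**The QMG trigger.** A reader might infer that, because the example retreatment trigger and the QMG responder threshold are both 3 points, borrowed scores will readily flip QMG response. The documents do not support that. If QMG rose by 3 points, a score recording the rise exists and would normally be the last available value. A flip needs a worsening that was not recorded on QMG. That is possible, because the trigger is only an example and is at the Investigator's discretion.

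**Direction.** A reader might infer that the rule inflates efficacy. The wording of 3.3 and 13.2, taken together, points to the last score, and borrowing a Day 43 score hides improvement. The opposite error needs 3.3 to be read as allowing an older score, such as the previous Day 1. Its wording leaves that open but does not direct it.

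**MG0004 entrants.** A reader might infer from Table 1-3 footnote b that their MG0004 final visit serves as cycle baseline however old it is. They enter at Visit 9 and have scheduled scores from then on, so the lead-in visit is reached only if every later pre-dose score is missing.

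**Conclusion.** The concern holds in limited form. When the rule is triggered as written, it can give a wrong change or responder result for that participant-cycle. For MG-C and QMG after a Table 1-3 cycle, this arises at restarts on nominal Days 64 to 98; for MG Symptoms PRO, through Day 155. Under the last-score reading the usual error is understated improvement. MG-C is most exposed. MG-ADL, the main efficacy endpoint, is least exposed because it is scheduled at every Table 1-3 visit.

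The overall size cannot be computed. The shifts of 0.03 to 0.30 points rest on assumed shares and an assumed 3-point gap, and the true effect is zero if no baseline is missing. The spans assume nominal visit days, no unscheduled score and no restart earlier than 4 weeks after the last dose. The primary endpoints are safety endpoints and nothing is tested, so no error rate or power is affected. The point is still worth correcting, because the rule is explicit, undisclosed in 3.9 and cheap to change.

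**What to change.** For the efficacy scales, in SAP 3.3 and 13.2:

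- Accept as cycle baseline only a pre-dose score from that cycle's Visit 1, or from a short look-back window before the cycle's first dose. The sponsor should state the window, and it must fall after the previous cycle's Day 43. Apply the limit to both baseline sentences in 3.3.
- Otherwise set that cycle's change and responder status to missing.
- Keep the lead-in EOS visit as baseline for the first cycle of direct MG0003 rollovers, as Table 1-2 footnote b provides. Reconcile Table 1-3 footnote b with the new rule for MG0004 entrants.
- List the rule in SAP 3.9, and report the number of affected participant-cycles per instrument.

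Section 3.3 also governs laboratory, vital-sign, ECG and IgG baselines. This proposal does not cover them, so the revised text should say that it applies to efficacy scales only.

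The cost is SAP wording and one count table. A probably small but unknown number of participant-cycles would leave the change and responder tables. SAP 3.1 already bases percentages on participants with observed data and displays the denominator, so the loss would be visible.

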3.4 Protocol deviations

Important protocol deviations (IPDs) are deviations from the protocol which potentially could have a meaningful impact on study conduct or on the key efficacy, key safety, or PK/PD outcomes (if applicable) for an individual participant. The criteria for identifying important protocol deviations will be defined within the appropriate protocol-specific document. Important protocol deviations will be reviewed as part of the ongoing data cleaning process and data evaluation.

3.5 Analysis sets

3.5.1 Enrolled Set

The Enrolled Set (ES) will consist of all study participants who have signed the informed consent form.

3.5.2 Full Analysis Set

The Full Analysis Set (FAS) will consist of all study participants in the ES who were randomized in this study or in MG0004. Study participants enrolling from MG0004 will utilize their last assigned dose level from MG0004 as their planned dose in MG0007.

3.5.3 Safety Set

The Safety Set (SS) will consist of all study participants in the FAS who received at least one dose of IMP in MG0007.

3.6 Treatment assignment and treatment groups

For the analyses using SS, FAS and ES by entire study and first dose received, study participants will be grouped according to the highest dose levels of IMP participants received in MG0007 first cycle (7mg/kg or 10mg/kg). If participants switched dose in first cycle of MG0007, then they will be assigned to IMP 10mg/kg group. For example, if a participant's highest dose in first cycle of MG0007 is IMP 10 mg/kg and then changed to 7 mg/kg in the next cycle, then the participant will still be allocated to 10 mg/kg for these analyses.

For the safety analyses using SS by entire study and most recent dose received (summary of adverse events), participants will be grouped according to the most recent dose level of IMP participants received prior to the onset of AEs. For example, if a participant's last dose prior to an AE is 10 mg/kg, then the participant will be allocated to 10 mg/kg for this AE.

For the analyses performed using SS and FAS by treatment cycle, participants will be grouped according to the highest dose levels of IMP participants received (7mg/kg or 10mg/kg) within

each cycle. If participants switched dose within one cycle, then they will be assigned to IMP 10mg/kg group for that cycle. For example, if for a participant, the highest does in first cycle is 10 mg/kg and the highest dose received in second cycle is 7 mg/kg, then the participant will be allocated to IMP 10 mg/kg and 7mg/kg respectively.

For participants who were not treated in FAS and ES, they will be assigned to 'Not Treated' group.

